the capsule by irrigation in addition to the manipulation of intracapsular structures (3,4). It has been established that multimodal analgesia yields best pain control as different pain pathways are targeted with different drugs and techniques with regional anesthesia being one of the most prominent modalities (5). For a long time interscalene block (ISB) has been used for shoulder scope surgeries. Although it is an effective block, the procedure is not devoid of complications which include phrenic nerve affection and diaphragmatic paralysis which could affect respiration. Also, dural spread and brachial plexus injury are among the recorded complications (6,7). Even when these complications do not occur, interscalene block affects motor power of the arm while PENG block spares motor power affection which is a key factor regarding that shoulder scopes are usually day case surgeries.

Interscalene block produces an intense motor block of the upper limb muscles which may extend to the hand muscles leading to the discomfort of patients and predisposing them to injuries (8), patients are always advised to carry the numb limb in an immobilizer and to protect it till complete sensory and motor function returns.

Therefore, alternatives for interscalene block as suprascapular nerve blocks or supraclavicular nerve blocks are being researched. Pericapsular nerve group (PENG) block is one of the novel techniques that are being studied currently, its main advantage over interscalene is that the target is the peripheral nerve endings around the joint capsule rather than tackling large nerves as the brachial plexus trunks (9). It has been first introduced in hip arthroplasty and other hip surgeries and showed promising results; thus, it is being applied to shoulder scope surgeries (10).

Papers have been published investigating the efficacy of PENG block in hip surgery with different control and comparison groups, as was done by Mosaffa F et al when comparing PENG with fascia iliaca compartment block (11). Other studies were done on PENG block efficacy in shoulder surgery, but with comparison against suprascapular nerve block, and with the main focus on postoperative pain relief as a primary outcome rather than recovery of motor power. To our knowledge, this is the first study to compare between the effect of PENG block and interscalene block on muscle power of the hand in shoulder arthroscopic surgery.

Aim of the work

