Patients in this study will be randomly assigned to one of two groups; Group A will receive PENG block and Group B will receive interscalene block. All patients will be evaluated preoperatively by routine lab investigations (full blood picture, serum electrolytes, liver and kidney function tests and coagulation profile).

Patients will be educated concerning the nature of the procedure and its possible complications, and all patients will sign a written informed consent. Short term fasting will be encouraged (6 hours for solid food, 2 hours for clear fluids). A 3rd generation cephalosporin will be given 30 min prior to the procedure as prophylaxis. Before admittance to the operation

theatre, a 22G cannula will be inserted and anxiolysis will be achieved by giving the patients midazolam 2 mg IV.

Upon arrival to the operation room, all patients will receive standard monitoring (Pulse oximeter, ECG, NIBP, Capnography), and baseline hemodynamic measurements of heart rate, systolic blood pressure (SBP), diastolic blood pressure (DBP) and mean arterial blood pressure (MAP) will be recorded. Also baseline muscle power of the hand on the same side of surgery will be measured using a digital dynamometer (Handeful Digital Hand Dynamometer, Handeful, CA, United States). The dynamometer we are using is a digital one that measures grip strength in kilograms.

Group P (PENG Block group):

Patients in this group will receive PENG block prior to induction of general anesthesia. Patient will be placed in supine position with arm abducted and externally rotated. Skin will be disinfected then under ultrasonic guidance (ACUSON X300™ ultrasound system, Siemens Medical Solutions, Inc, Germany) a high frequency linear ultrasound probe (12MHz) will be applied longitudinally between the head of humerus and coracoid process then local infiltration will be done using 29 G needle to apply 3 mL lidocaine 2%. After identification of deltoid muscle and subscapularis muscle tendon which should be immediately superficial to humeral head, a 22-gauge needle (SonoPlex® STIM, PAJUNK® Medical System L.P., Germany) will be advanced to pierce the deltoid and target the tip to be just touching the subscapularis tendon. A test dose of 3 ml saline solution will be injected to visualise the separation of deltoid from subscapularis and confirm and the

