needle is in the correct position. Afterwards 15 ml of 0.25% bupivacaine will be injected to complete the block. A wait time of 30 minutes will be allowed before induction of general anesthesia to ensure the full activation of the block.

Group I (Interscalene block):

Patients in this group will also receive ISB prior to general anesthesia. With patient placed in supine position and head facing away from the side being blocked, the skin is disinfected first then the linear ultrasound probe is placed transversely on the neck to identify the carotid artery. Then the transducer is moved slightly laterally until middle and anterior scalene muscles are identified with the brachial plexus between them then local infiltration will be done using 29 G needle to apply 3 mL lidocaine 2%. A 22-gauge needle will be introduced in plane in a lateral-medial direction aiming towards the space between the roots. After a 3 ml saline injection for confirmation of proper position, 15 ml of 0.25% bupivacaine will be injected with advancement of the needle as the roots are displaced by the injectate. Adequate injection will be confirmed by visualizing the roots being surrounded by the local anesthesia infiltrate.

Patients receiving either block will wait 30 minutes before induction of general anesthesia. Interscalene block will be tested using pin prick test on shoulder and upper arm area, by loss of shoulder abduction, and finally by passively moving the arm to check for loss of previously present pain on movement. PENG block will be tested using pin prick test and loss of pain on passive movement as well. A block not fulfilling these examinations will be

deemed unsuccessful, and the patients will be given additional opioids in the form of morphine 5 mg IV with induction of general anesthesia. These patients will be excluded from the study. Before induction of general anesthesia another dynamometer measurement will be recorded.

In both groups patients will receive general anaesthesia using the standard centre preferences; IV induction via propofol 2 mg/kg and fentanyl 1 mic/kg for induction, then atracurium 0.5 mg/kg for intubation followed by 0.1 mg/kg every 20 minutes for maintenance. An additional dose of fentanyl 1 mic/kg will be administered on skin incision.

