For maintenance of anaesthesia, isoflurane will be administered at a concentration of 1.2-2%, and the patient will be mechanically ventilated using parameters that will achieve normal end-tidal CO₂ (35-45 mmHg) and oxygen saturation (> 95%). To maintain relaxation atracurium will be given as 0.1 mg/kg every 20 minutes.

Intraoperative hemodynamics will be measured at 10 min intervals, both heart rate and blood pressure values (SBP, DBP and MAP) will be recorded. Bradycardia defined as heart rate below 60 beats per minute, and bradycardia will be managed if heart rate drops below 55 bpm by giving atropine 0.04 mg/kg IV bolus to be repeated after 5 minutes if needed. Hypotension also described as SBP below 90 mmHg will be managed by giving ephedrine 5-10 mg IV bolus.

At the end of surgery, patients will be given 1 g acetaminophen IV, and NSAID will be given in the recovery room in the form of ketorolac 30 mg IV.

For recovery, neuromuscular blockade will be reversed using neostigmine 0.04 mg/kg and atropine 0.02 mg/kg, and the patient will be extubated fully awake and when adequately reversed which is clinically assessed as the patient achieves tidal volumes > 5ml/kg.

Patients will be transferred to the post anesthesia care unit (PACU), and same intraoperative hemodynamics will be measured every 10 min through their PACU stay duration. With regards to postoperative management, Visual analog scale (VAS), which is a scale from 0 to 10 where 0 represents no pain at all and 10 represents the most severe pain, will be used to assess pain. VAS assessment will be carried out during the 1st hour at the PACU then at 2, 4, 6, 12, and 24 hours postoperative during day 1, and If VAS is >4, opioids will be administered in the form nalbuphine 5mg IV, and the time to first dose and total number of doses given will be noted not to exceed 60 mg per day. Also, hand grip power will be assessed at the PACU then at 2, 4, 6, 12, and 24 hours postoperatively, and this will be done using the digital dynamometer. The readings will be compared with a measurement of the patient's baseline grip power of the same hand taken before surgery and with readings taken after block administration.

3. Measurement tools

- Hand grip power will be measured using digital dynamometer at these intervals: immediately postoperative at PACU and then at 2, 4, 6, 12, and 24 hours postoperative, and results compared with baseline measurement.
- Time for full recovery of hand grip power.

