- Intraoperative hemodynamics in the form of heart rate and mean blood pressure every 10 minutes.
- Postoperative pain will be measured using VAS score at these intervals: immediately postoperative at PACU and then at 2, 4, 6, 12, and 24 hours postoperative.
- Postoperative hemodynamics in the form of heart rate and mean blood pressure in PACU every 10 minutes until discharge
- Time to first opioid dose
- Total amount of opioid administered.
- Patient satisfaction will be measured at 24 hours postoperative using self reported satisfaction scale (1= very dissatisfied and 5=very satisfied)

VI. Study outcomes

1. Primary outcome

- Time for full recovery of hand power, defined as time from start of block activation till time of achieving grip strength similar to patient's baseline

2. Secondary outcome(s)

- Hand grip power after surgery at PACU, then at 2, 4, 6, 12, and 24 hours.
- Time to first analgesia request
- VAS score after surgery at rest and during movement at PACU then at 2, 4, 6, 12, and 24 hours

- Patient satisfaction score at 24 hours postoperative
- Intraoperative hemodynamics

Statistical Analysis

I. Sample size

Based on a previous study (12) the duration of motor block in patients receiving ISB was 711 ± 151 min (REF). A minimum sample of 50 patients is needed to detect a 20% reduction in duration of motor block. The study power was set at 90% and alpha error was set at 0.05. Sample size was calculated using the MedCalc Software V14. The number of envelopes will be increased to 60 (30 in each group) to compensate for dropouts.

II. Statistical analysis

Statistical package for social science (SPSS) software, version 26 for Microsoft Windows (SPSS inc., Chicago, IL, USA) will be used for data analysis. Categorical data will be presented as frequency (%) and will be analyzed by the chi square test. Continuous data will be checked for normality using the Shapiro-Wilk test and will be presented as mean (standard deviation) or median (interquartile range) as appropriate. Continuous data will be analyzed using unpaired the t test or the Mann Whitney test according to normality of the data. Repeated measures will be analyzed using the analysis of variance (ANOVA) for repeated measures with post-hoc pairwise comparisons using the Bonferroni tests. A P-value less than 0.05 will be considered statistically significant.

References

- (1) Farmer KW and Wright TW. Shoulder arthroscopy: the basics. *J Hand Surg Am.* 2015 Apr; 40(4):817-21.

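### Serial grip strength would be compared between arms without adjusting for the pre-block grip reading already collected from each patient

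*Combined protocol and SAP*

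**What the plan says.** Section VI.2 (Secondary outcomes) lists "Hand grip power after surgery at PACU, then at 2, 4, 6, 12, and 24 hours", which gives six postoperative readings. Section V.2 (Study Protocol) provides the baseline, taken on arrival in the operating room and before the block: "Also baseline muscle power of the hand on the same side of surgery will be measured using a digital dynamometer". A second preoperative reading follows the block: "Before induction of general anesthesia another dynamometer measurement will be recorded".

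Section V.3 (Measurement tools) says the grip readings are taken "and results compared with baseline measurement", and V.2 says much the same. Neither says how.

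Under Statistical Analysis, II, the only sentence that fits a serial continuous outcome is "Repeated measures will be analyzed using the analysis of variance (ANOVA) for repeated measures with post-hoc pairwise comparisons using the Bonferroni tests". Other continuous data go to a t test or Mann-Whitney test. No covariate, ANCOVA, change score or percentage of baseline is mentioned for any outcome.

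The primary outcome in VI.1 does use the patient's own baseline, because recovery time runs "till time of achieving grip strength similar to patient's baseline". This point concerns only the serial readings.

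**The concern.** The aim of the trial is to compare the effect of the two blocks on hand motor power, and serial grip measures that directly. Grip differs between patients before any block is given. If part of that difference persists after surgery, an analysis that ignores baseline leaves it in the error term.

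The stated comparison with baseline does not settle the matter. Carried into a repeated-measures ANOVA, it would most naturally become a change score or an extra time level, and neither adjusts the between-arm contrast for baseline as a covariate. At stake are the width of the confidence intervals and exposure to chance baseline imbalance. Because the plan leaves the form open, it could also be chosen after the data are seen.

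**Working it through.** **The plan's own figure.** The sample size concerns the primary outcome. The difference is 0.20 × 711 = 142.2 min, with SD 151, two-sided alpha 0.05 (sidedness assumed) and power 90%. The t-test calculation gives 25 per arm, N = 50 (power 90.4%), so the stated minimum reproduces. Sixty envelopes allow 10/60 = 16.7% dropout. None of this depends on serial grip.

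**Inputs for grip.** 25 analysed patients per arm (from the plan). The correlation r between pre-block and follow-up grip is not in the documents; 0.3, 0.5 and 0.7 are assumed.

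**Variance of the between-arm difference at one time, equal SDs,** relative to an unadjusted comparison:
- change score: 2(1 − r)
- baseline as covariate: 1 − r²
- covariate against change score: (1 − r²) / [2(1 − r)] = (1 + r)/2

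Confidence-interval width goes with the square root.

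| r | Variance vs unadjusted | CI width | Variance vs change score | CI width |
|---|---|---|---|---|
| 0.3 | 0.91 | 0.954 (5% narrower) | 0.65 | 0.806 (19% narrower) |
| 0.5 | 0.75 | 0.866 (13%) | 0.75 | 0.866 (13%) |
| 0.7 | 0.51 | 0.714 (29%) | 0.85 | 0.922 (8%) |

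**Small-sample cost.** Estimating the slope multiplies the variance by about 1 + 1/(N − 4) = 1 + 1/46 = 1.022. Break-even with unadjusted: (1 − r²) × 1.022 = 1, so r is about 0.15. Break-even with change scores: (1 + r)/2 × 1.022 = 1, so r is about 0.96. At r = 0 the cost against unadjusted is about 2% in variance.

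**Simulation** (40,000 runs, 25 per arm, ANCOVA at each time, which equals the mixed model when data are complete). With equal SDs the variance ratios were 0.93, 0.77, 0.52 against unadjusted and 0.66, 0.77, 0.87 against change scores, close to the formulas.

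**Dense-block case.** The background warns that "Interscalene block produces an intense motor block of the upper limb muscles which may extend to the hand muscles". Assume that interscalene follow-up grip has 25% of the baseline SD and no correlation with baseline, and that PENG grip keeps its SD and correlation r. The simulated variance ratios are:
- against unadjusted: 0.98, 0.91, 0.80, so CIs 1%, 5%, 11% narrower
- against change scores: 0.42, 0.46, 0.50, so CIs 35%, 32%, 29% narrower

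**Baseline as a seventh time level.** The group main effect is diluted to 6/7. Under compound symmetry, its variance for the same effect, relative to the mean of the six postoperative readings, is {[(1 + 6r)/7] / (6/7)²} / [(1 + 5r)/6]. At r = 0.5 this is 0.778/0.583 = 1.33; it runs from 1.31 to 1.36 for r from 0.3 to 0.9.

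**Chance imbalance.** With 25 per arm the standard error of the baseline difference is √(2/25) = 0.28 SD, and the probability that it exceeds 0.3 SD in either direction is 29%.

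**The case against.** The strongest reply is that this is a refinement. Repeated-measures ANOVA is a valid comparison in a randomised trial, the outcome is secondary, and no power claim rests on it. The plan is also silent rather than wrong: it assigns no method to grip by name, and it does intend some comparison with baseline. All of that is true. It limits the point to precision and pre-specification but does not remove it, because every continuous-data method in the plan lacks a covariate.

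A second reply is that the plan's timings favour the small gain. Adding the 30-minute wait, 90 to 120 minutes of surgery and 360 minutes puts the 6-hour reading 480 to 510 minutes after the block, ignoring turnover. That is (711 − 510)/151 = 1.3 to (711 − 480)/151 = 1.5 SD before the mean interscalene duration used for the sample size. If that duration applies to grip, four of the six readings fall while most interscalene patients are still blocked. There the gain over an unadjusted analysis is 1% to 11% under the dense-block assumptions, and the between-arm difference may be too large for precision to matter. This stands: the benefit lies mainly at 12 and 24 hours. The largest figures, 29% to 35%, apply only if change scores are used, which the plan does not state.

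Third, the equal-SD percentages come from large-sample formulas. The simulated ratios give about one percentage point less in most cases. The difference is immaterial.

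Fourth, an unstructured covariance for six times has 6 × 7/2 = 21 parameters, which is demanding for 50 to 60 patients. That is fair, and it is why a fallback is needed.

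**Conclusion.** The point holds. As written, and reading the repeated-measures sentence as covering grip, the plan compares serial grip between arms without covariate adjustment for a baseline it collects. The cost is precision on one secondary outcome, not bias.

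The size rests on an assumed correlation. For r from 0.3 to 0.7, confidence intervals would be 5% to 29% narrower than unadjusted with equal SDs, and 1% to 11% narrower while one arm is densely blocked. The worst case considered, r = 0, costs about 2% in variance. That balance favours adjustment, and the change should be made, but the trial's main conclusion does not depend on it.

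**What to change.** State in Statistical Analysis, II, that the six postoperative grip readings will be analysed with a linear mixed model: group, time, group by time, pre-block grip and pre-block grip by time, with unstructured covariance.

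- **Covariate.** Use only the pre-block reading. The reading before induction follows the block and is already affected by treatment.
- **Missing readings.** Use all available readings, so that one missed reading does not drop a patient, as it does in standard repeated-measures ANOVA. This does not address the rule for failed blocks ("These patients will be excluded from the study"), which defines the analysis set and is a separate question.
- **Reporting.** Give the adjusted PENG minus interscalene difference at each time. The plan does not say which pairs its Bonferroni tests compare. If they are the six between-arm contrasts, the matching intervals have level 1 − 0.05/6 = 99.2%; otherwise give 95% intervals labelled as unadjusted for multiplicity.
- **Unequal spread.** Check residuals. If one arm is near zero grip, use arm-specific residual variance or robust standard errors. In the dense-block simulation, coverage of the equal-variance 95% interval was 94% to 95% at 25 per arm, but 92% to 93% with 22 PENG and 28 interscalene patients. Arm-specific variance restored about 95%.
- **Fallback.** If the model does not converge, use ANCOVA at each time with the same covariate.

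The cost is wording and slightly more analysis work. SPSS, already named, fits the model. Bonferroni-matched intervals are about 37% wider than 95% intervals (t with 47 degrees of freedom: 2.75/2.01 = 1.37).

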The aim of the study is to compare the effect of PENG block and interscalene block on the motor power of the hand and time to full recovery of motor affection if any.

Objectives:

- To assess effectiveness of PENG block in recovery of hand motor power compared with ISB
- To compare between PENG and ISB in controlling postoperative pain
- To assess effectiveness of PENG block in reducing postoperative opioid consumption compared with ISB

Hypothesis

We hypothesize that PENG block will be superior to interscalene nerve block regarding motor power sparing.

Ethical Considerations

This study will be conducted after taking approval of the research ethical committee. Written informed consent will be obtained from study participants or their legally authorized representative.

Methodology

I. Study design

Randomised comparative single blinded superiority study.

II. Study setting and location

This study will be conducted at the theatre for orthopedic surgeries at The Cairo University Teaching Hospital.

III. Study population

Patients scheduled for arthroscopic shoulder surgery

IV. Eligibility Criteria

1. Inclusion criteria

- Adult patients (age 22-60) scheduled for arthroscopic shoulder surgery under general anesthesia
- Both genders
- ASA grade I-II
- BMI less than 35
- Duration of surgery 90-120 minutes

2. Exclusion criteria

- ASA grade III-IV
- Allergy to local anesthetics
- Coagulation disorder (INR >1.2, Platelets <100,000), or recent intake of clopidogrel or warfarin within 1 week.
- Active infection at site of injection

V. Study Procedures

1. Randomisation

This is a single centre randomised comparative trial. Patients undergoing arthroscopic shoulder surgery will be randomised to receive either PENG block, which is the intervention group, or to receive interscalene block.

Randomisation will be done via computer generated random numbers which will be enclosed in envelopes with 60 envelopes in total, 30 for each group. This is a single blinded study so an anesthesiologist who will not partake in this study will open the envelopes and proceed with the allocated block. After the procedure, the anesthesiologist who will assess motor power recovery and collect postoperative data will also be blinded to the type of block given. Therefore, to reduce bias only the anesthesiologist and main researchers will be aware of the allocation, while the outcome data collector will be blinded.

2. Study Protocol

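### Repeated-measures ANOVA suits the serial secondary data poorly: it must drop patients or readings in the haemodynamic series, and no rule covers missed readings or non-sphericity

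*Combined protocol and SAP*

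**What the plan says.** All places are in the combined protocol and SAP.

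- **Method** (Statistical Analysis, II): "Repeated measures will be analyzed using the analysis of variance (ANOVA) for repeated measures with post-hoc pairwise comparisons using the Bonferroni tests". The section does not say which effect is tested (group, time or group-by-time). It gives no sphericity check or correction, no rule for missed readings and no common time window. The software is SPSS 26, with no procedure named.
- **Intraoperative haemodynamics**, a listed secondary outcome: "Intraoperative hemodynamics will be measured at 10 min intervals" (V.2 Study Protocol). The inclusion criteria set "Duration of surgery 90-120 minutes".
- **PACU haemodynamics**: "Postoperative hemodynamics in the form of heart rate and mean blood pressure in PACU every 10 minutes until discharge" (V.3 Measurement tools). This series is not among the outcomes in section VI.
- **Grip**, secondary outcome: "Hand grip power after surgery at PACU, then at 2, 4, 6, 12, and 24 hours".
- **VAS**, secondary outcome: "VAS score after surgery at rest and during movement at PACU then at 2, 4, 6, 12, and 24 hours".

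**The concern.** Classical repeated-measures ANOVA needs a value in every cell. It also assumes sphericity: differences between any two times must all have the same variance. The plan's schedule strains both conditions, in two separate ways.

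First, both haemodynamic series have patient-specific lengths, so a complete rectangular data set exists only if short series are dropped or long ones cut. Grip and VAS are rectangular by design, but one missed reading removes the whole patient.

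Second, readings close in time usually correlate more than readings far apart. Grip and VAS gaps widen from about an hour to 12 h, and haemodynamics are read in close succession. Sphericity is then unlikely, and an uncorrected group-by-time F-test rejects too often.

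What is at stake is precision in the secondary comparisons and, if that uncorrected test is used, its error rate. Grip and VAS bear on the stated objectives for hand motor power and postoperative pain.

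**Working it through.** **1. The plan's own figure.** The only stated sample size is 50, for duration of motor block: mean 711 min, SD 151, 20% reduction, power 90%, alpha 0.05 (two-sided assumed). The difference is 0.20 × 711 = 142.2 min. The normal formula gives 24 per arm (48). The exact t calculation gives 25 per arm (50, power 0.904), which reproduces the plan. This figure belongs to the primary outcome, one time per patient, and does not depend on the ANOVA sentence.

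**2. Length of the intraoperative series.** 90/10 = 9 and 120/10 = 12, so about 9 to 12 readings per patient (10 to 13 with a time-zero reading), if timed from the start of surgery. The documents give no distribution of duration. If it were uniform on 90 to 120 min, the share with a reading at time t is (120 − t)/30: 100% at 90 min, 67% at 100 min and 33% at 110 min. A cut at 90 min keeps every patient and loses the later readings. Any longer window loses patients.

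**3. Complete cases through missed readings.** The documents give no missingness rate. If each of k readings is missed independently with probability m, then 60 × (1 − m)^k patients remain:

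| m per reading | k = 6 (grip, VAS) | k = 9 | k = 12 |
|---|---|---|---|
| 1% | 56.5 | 54.8 | 53.2 |
| 2% | 53.2 | 50.0 | 47.1 |
| 5% | 44.1 | 37.8 | 32.4 |

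For six readings at 3%: 60 × 0.97^6 = 60 × 0.833 = 50.0.

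**4. Type I error of the group-by-time test.** Null trials were simulated with 30 per arm and 8,000 runs per scenario. Correlation was r^|gap|, with the gap in hours for grip and VAS (times 1, 2, 4, 6, 12 and 24 h, PACU taken as 1 h) and in 10-min steps for haemodynamics. The uncorrected test refers F = [SS(interaction)/(k − 1)] / [SS(error)/((N − 2)(k − 1))] to k − 1 and (N − 2)(k − 1) degrees of freedom. The Greenhouse-Geisser version multiplies both by the estimated epsilon. Monte Carlo standard error at 5% is √(0.05 × 0.95/8000) = 0.24 percentage points.

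| Series | r | epsilon | Uncorrected | Corrected |
|---|---|---|---|---|
| Grip/VAS, 6 | 0.5 | 0.915 | 5.3% | 4.3% |
| | 0.7 | 0.808 | 6.5% | 5.0% |
| | 0.9 | 0.580 | 8.5% | 5.2% |
| | 0.95 | 0.488 | 9.3% | 4.9% |
| Haemodynamics, 9 | 0.5 | 0.705 | 7.4% | 4.5% |
| | 0.7 | 0.521 | 9.3% | 4.7% |
| | 0.9 | 0.362 | 10.8% | 4.7% |
| Haemodynamics, 12 | 0.5 | 0.673 | 8.4% | 4.8% |
| | 0.7 | 0.466 | 10.5% | 5.2% |
| | 0.9 | 0.290 | 12.5% | 5.0% |

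The between-group main-effect test stayed between 4.4% and 5.2% throughout.

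**5. Does losing patients cause the inflation?** No. With sphericity true (equal correlation 0.5), the uncorrected test gave 4.7% with complete data and 4.4% with 5% of readings missing and incomplete patients dropped (mean N 44). At r = 0.9 the figures were 8.5% complete and 8.1% after the same loss.

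**The case against.** The strongest reply is that the plan is brief rather than wrong. It names no interaction test and does not rule out a correction. A Greenhouse-Geisser correction restores the error rate, a 90-min window equalises the intraoperative series, and two added sentences would largely suffice. Every magnitude above rests on an assumed missingness rate, correlation or duration distribution. At 1% to 2% missed, 53 to 56 of 60 patients remain for grip and VAS. Most of this stands, and it keeps the point to secondary and supporting analyses. It does not remove the point: neither repair is prespecified, and neither keeps a patient who misses a reading.

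Several stronger readings are tempting but unsupported:

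- *Unequal series or lost patients make the interaction test liberal.* Step 5 shows otherwise. Non-sphericity without correction does.
- *The group-by-time P-value will be too small.* This holds only if that test is run uncorrected, which the plan leaves open.
- *44 patients falls below a required 50.* The 50 is for the primary outcome. No sample size is stated for any serial outcome.
- *Operation length affects every serial outcome.* It sets the length of the intraoperative series only; PACU series vary with discharge. Grip and VAS have fixed times.
- *Only 20 of 60 patients would be analysed.* That is 33% of 60 for an ANOVA run to 110 min, which nobody specified, under an assumed uniform duration.
- *The randomised comparison is lost.* Bias would need duration or missingness to be related to arm or outcome. The documents show no such link.

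**Conclusion.** The point holds for the secondary and supporting analyses. By the plan's own figures, the ANOVA cannot use the intraoperative haemodynamics (about 9 to 12 readings) in full: it must drop patients with shorter series or discard later readings. The same applies to PACU haemodynamics. For grip and VAS the loss depends on missed readings: about 56, 50 or 44 of 60 patients remain at an assumed 1%, 3% or 5%, missed independently.

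The sphericity problem is a separate, conditional risk. If a group-by-time F-test is used uncorrected, type I error is about 5% to 9% for grip and VAS and about 7% to 12% for haemodynamics, under the assumed correlations. The change is worth making because it is cheap and the serial outcomes serve stated objectives, but it does not threaten the trial's main conclusion.

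**What to change.** Replace the ANOVA sentence in Statistical Analysis, II with text to this effect:

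> Serial outcomes will be analysed with a linear mixed model (SPSS MIXED) with arm, time as a category and arm-by-time as fixed effects, using all available readings. Covariance will be unstructured for grip and VAS and autoregressive for the 10-min haemodynamics. The PENG minus ISB difference at each time will be reported with its 95% CI.

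This keeps every patient with at least one reading and does not assume sphericity. The cost is SAP wording and slightly more analysis work in the same software, with no new data. It relies on readings being missing at random and on a reasonable covariance choice; residuals should be checked for the 0 to 10 VAS. The simulation above did not test the mixed model itself.

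If ANOVA is kept, the minimum is to prespecify a Greenhouse-Geisser correction and a common haemodynamic window, and to state how missed readings are handled. That repairs the error rate and equalises the haemodynamic series, but incomplete patients are still lost.
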